A Prospective, Randomized, Multicenter, Open-Label, Pilot Study to Investigate Medication Adherence & Patient Reported Symptom Occurrence & Interference w/ Daily Life Comparing Envarsus XR® & Immediate Release Tacrolimus in Adult Renal Transplant Recipients (SIMPLE)

NCT03979365

08April2021

Clinical Study Protocol [#SIMPLE]

CLINICAL STUDY PROTOCOL

A Prospective, Multicenter, Open-Label, Observational Pilot Study to Investigate Medication Adherence and Patient Reported Symptom Occurrence and Interference with Daily Life Comparing Once-Daily Envarsus XR® and Twice-Daily Immediate Release Tacrolimus in Adult Renal Transplant Recipients (SIMPLE)

Clinical Coordination & Data Management

[name].

Principal Investigator – Lead Site

Multicenter Transplant Alliance – Director
Department of Surgery and Immunology
Mayo Clinic
Rochester, MN

Protocol Version: 3.0

Date: 08APR2021

Clinical Study Protocol [#SIMPLE]

Participating Centers of the Multicenter Transplant Alliance (MTA)

Henry Ford Hospital

Investigators: [name]. and [name].

Mayo Clinic Arizona

Investigator: [name].

Mayo Clinic Jacksonville

Investigator: [name].

Mayo Clinic Rochester

Investigators: [name]. and [name].

Biostatistician: [name]., M.S.

Terasaki Research Institute (TRI)

Investigators: [name]. and [name], M.S.

Washington University St. Louis

Investigators: [name]. and [name], M.S.

Clinical Study Protocol [#SIMPLE]

SYNOPSIS

Title: A Prospective, Multicenter, Open-Label, Observational Pilot Study to Investigate Medication Adherence and Patient Reported Symptom Occurrence and Interference with Daily Life Comparing Once-Daily Envarsus XR® and Twice-Daily Immediate Release Tacrolimus in Adult Renal Transplant Recipients (SIMPLE)

Name of Products Studied: Envarsus XR® and tacrolimus (twice daily formulation)

Study Center(s): Multicenter Transplant Alliance – Kidney Centers

Study Design: Prospective and observational

Study Period (years):

Estimated date of first subject enrolled: May 2019

Estimated date last subject to complete the study (12 month follow-up): May 2021

Enrollment Rationale: The Multicenter Transplant Alliance Kidney Consortium collectively transplants more than 1,500 people each year (10% of the total number of kidney transplants in the United States annually). Approximately 60% of these patients will be eligible for this study. We consider a 12 month enrollment time to be a conservative estimate.

Study Background:

Despite improvement in short-term graft outcomes in organ transplant, transplant patients still have to take on complex medication regimens to achieve current results. Adherence to these complex medications is an important problem in light of the potential risk of acute and chronic rejection and the associated burden of increased hospitalization, cost, and diminished quality of life that results from missed doses and poor overall drug taking. Part of the diminished quality of life is also tied to the bothersome symptoms patient feel after transplant. Most patients experience symptoms that relate to either the overall transplant immunosuppression or medication specific side effects. In the BENEFIT and BENEFIT-EXT trials, >60% of patients reported tiredness and lack of energy as an issue¹. Sleep problems, mood swings, restlessness, anxiety, depression, and concentration and memory difficulties appeared in approximately 50-60% of patients. In addition to these symptoms, >38% patients also reported numerous others side effects that have been strongly associated with calcineurin-inhibitors such as tacrolimus that include dizziness, muscle cramps, trembling hands, tingling in hands and feet, and headache.

Study Rationale:

We hypothesize that the use of once-daily Envarsus XR® leads to a decrease in some transplant- and tacrolimus-related adverse symptoms and potentially leads to improvement in quality of life and medication adherence when compared to twice-daily tacrolimus. In order to assess this hypothesis, a prospective, multi-center, open-label, observational, pilot study to investigate medication adherence and patient reported symptom occurrence and interference with daily life comparing once-daily Envarsus XR® and twice-daily immediate release tacrolimus in adult renal transplant recipients (SIMPLE) is being proposed.

The primary objective of this study is to compare tacrolimus formulations (Envarsus XR® versus twice a day tacrolimus) with the hypothesis that Envarsus XR® improves transplant- and tacrolimus- associated symptoms when compared to a twice a day tacrolimus regimen. In addition, as part of this study,

Clinical Study Protocol [#SIMPLE]

adherence, additional patient reported outcomes (PROs), patient satisfaction, and health related quality of life (HRQoL) will be measured. There is currently a limited amount of data available describing the side effects/symptoms that are most important (i.e. occur most often and are poorly tolerated) to transplant patients taking tacrolimus immunosuppression. These symptoms/side effects could clearly impact medication adherence. Furthermore, no data currently exists as to how these symptoms/side effects relate to adherence, quality of life, and patient satisfaction. This study will assess the correlation between adherence, PROs, patient satisfaction, and health related quality of life (HRQoL). It is also possible that if the increase in adherence is large enough; there could be a sufficient change in long-term patient risk for antibody mediated injury and subsequent decrease in hospitalization and cost.

Study Design Rationale:

Patients will be enrolled into the study within the first 30 days post-transplant. Treatment will not be determined by this protocol, and there is no intervention. The treatment decision will be made by each patient's transplant care team, independent of the study.

For the primary objective, comparison of calcineurin inhibitor related symptoms, a standard two-group design will be used to compare treatment groups. These groups will also be compared for transplant-related symptoms, health-related quality of life, adverse events, patient satisfaction, adherence, and graft function.

Products Studied:

- Tacrolimus (twice daily immediate release (IR) oral formulation) or
- Envarsus XR® (a once daily extended-release oral tacrolimus formulation).

Envarsus XR® is an FDA approved medication and is indicated for the prevention of organ rejection in de novo kidney transplant patients in combination with other immunosuppressants.

Primary Objective: The primary objective of the study is to determine if patients taking Envarsus XR® report fewer of the side effects that are commonly associated with calcineurin-inhibitor therapy than subjects taking tacrolimus immediate release twice daily.

Primary Endpoint: Difference in mean calcineurin inhibitor-related symptoms severity score at 12 months post- kidney transplantation in the Envarsus XR® group vs immediate-release, twice-daily tacrolimus group.

The CIRS is a questionnaire that assesses five symptoms (from PRO-CTCAE) that have been shown to be associated with calcineurin inhibitors. These symptoms include trembling hands, muscle cramps, muscle weakness, swollen gums, and increased hair growth. Each symptom is based on symptom severity in the last 7 days scaled from 0 (none) – 4 (very severe). The cumulative score ranges from 0-20. Based on internal data, we expect a mean CIRS score in the control group (immediate release tacrolimus) to be around 3.8 +/- 3.6 and hypothesize a 30% reduction in the Envarsus XR® group. This reduction is equivalent to a 1 point difference on the 0-20 scale or a standardized effect size (mean difference / standard deviation) of 0.29.

Clinical Study Protocol [#SIMPLE]

Secondary Endpoints:

1. Reduction in the population mean of any one of the five individual CIRS item including: trembling hands, muscle cramps, muscle weakness, swollen gums, and increased hair growth between the two treatment groups at 12 months
2. Total percent of patients in each treatment group with a severe or very severe score (3 or 4) on any CIRS item 12 months.
3. Total percent of patient with a reduction in a CIRS item score from a severe or very severe score (3 to 4) to a mild to moderate (1 or 2) score from 4 to 12 months.
4. Total percent of patients with a reduction in any single CIRS item by 1 point or greater from 4 to 12 months.
5. Difference in mean transplant-related symptoms (TRS) score between treatments at 12 months post-transplant.

The TRS is a multi-item questionnaire capturing 15 symptoms (from PRO-CTCAE) that have been shown to be associated with transplant and general health-related quality of life improvement. These symptoms include change in taste, constipation, diarrhea, swelling in arms or legs, palpitations, dry skin, darkening of skin, blurry vision, headache, insomnia, anxiety, sadness, discouraged, increase in appetite, and fatigue. Each symptom is based on symptom severity in the last 7 days and scaled from 0 (none) – 4 (very severe). Some symptoms also have added questions pertaining to frequency and/or interference with daily activities. The sum of the severity score ranges from 0-60. The improvement in transplant symptoms will be measured by the difference between treatment groups in the mean TRS score.

6. Improvement in health-related quality of life (HRQoL), as measured by the PROMIS-29 health profile, will be compared between groups at 12 months post-kidney transplantation. The PROMIS-29 produces scores for depression, anxiety, fatigue, pain interference, sleep disturbance, physical function, participation in social roles, and pain intensity. Physical and mental health summary scores will also be calculated.

Standardized effect sizes (mean difference / standard deviation) for differences in HRQOL (PROMIS-29) scores will be calculated to compare twice daily immediate release tacrolimus oral to Envarsus XR®.

7. Improvement in individual symptoms captured in the TRS questionnaire will be compared.

The standardized effect size (mean difference / standard deviation) on TRS score will be calculated and compared between treatments. Individual TRS items will be classified as improved, worsened, unchanged and compared between treatments.

8. Improvement in overall tolerability or patient bother due to side effects, measured by item GP5 (“I am bothered by side effects of treatment”) from the FACT-G.

Patients’ GP5 responses will be classified as improved, worsened, or unchanged and compared between treatments.

9. Improvement in mean taking adherence, defined as the percent of prescribed doses taken each day (as measured by electronic monitoring), rates between groups.

Clinical Study Protocol [#SIMPLE]

The assumption is that the mean taking adherence will 75% for the twice-daily immediate release tacrolimus and 90% for the Envarsus XR® (and standard deviations of 38% and 30%, respectively).

10. Improvements in patient medication satisfaction as assessed by Transplant Satisfaction Questionnaire for Medication (question 14) at 12 months post-transplant.

Responses to the Transplant Satisfaction Questionnaire for Medication (question 14) will be compared between twice daily immediate release tacrolimus oral and Envarsus XR®.

11. Correlation between de novo DSA (dnDSA, collected as part of standard of care in MTA-K) and degree of taking and timing adherence.

Proportion of patients at different adherence thresholds ($>70\%$ vs $\leq 70\%$, $>80\%$ vs $\leq 80\%$, $>90\%$ vs $\leq 90\%$, and 100% vs below 100%) of taking and timing adherences between 4 months and 12 months post-transplant will be correlated with the presence or absence of dnDSA by 12 months post-transplant.

12. Safety and tolerability of Envarsus XR, as measured by incidence of adverse events (AEs), changes in clinical safety labs, and hospitalizations.

Difference between treatment groups in safety parameters including the incidence of adverse events (AEs), changes in clinical safety labs, and hospitalizations.

Inclusion criteria

Each patient must meet all of the following inclusion criteria to be enrolled in the study:

- Patient is an adult (18 years of age or older).
- Treatment with Envarsus XR® or immediate-release, twice-daily tacrolimus has been indicated by patient's transplant care team.
- Patient is a recipient of a deceased or living donor kidney transplant.
- Patient is able to comply with study procedures for the entire length of the study.
- Patient has been informed about the study survey and has signed an informed consent form.

Exclusion criteria

Patients meeting any of the following exclusion criteria are not to be enrolled in the study:

- Patient is unable or unwilling to complete study patient reported outcome questionnaires.
- Patient is currently receiving azathioprine
- Patient is currently receiving an mTOR inhibitor (sirolimus, everolimus)
- Patient is currently receiving belatacept
- Patient has received investigational immunosuppression 1 month prior to transplant or post-transplant
- Patient is in a setting where a professional care taker is responsible for dispensing subject's medication.

Study Duration

Following enrollment, each patient will be maintained in the study for 12 months.

Clinical Study Protocol [#SIMPLE]

Number of Patients

A total of 240 patients will be enrolled for the study. The enrollment will occur over a 12 month period. The average monthly enrollment will be 20 patients per month.

Study Design and Methodology

This is a prospective, multi-center, open-label, observational study comparing transplant-specific patient reported outcomes and medication adherence between Envarsus XR® and immediate release tacrolimus medication in adult renal transplant recipients. The study will enroll 240 patients and survey these patients at baseline (first 30 days post-transplant), at 4 months, and at 12 months post-transplantation.

Study Method

- Adverse Events: During the entire study period, each patient will be monitored at least monthly for trough blood levels, and undergo safety and adverse event assessments as per standard of care. The patient will be followed as appropriate to maintain the tacrolimus trough drug levels of 8 to 10 ng/ml in the first month post-transplant and 6 to 8 ng/ml thereafter.
 - AEs and SAEs will be assigned based on Common Toxicity Criteria for Adverse Events (CTCAE) definitions and tabulated as incidence rates per tacrolimus formulation.
 - Regular monitoring and summaries of hematology, blood chemistries, and urine results.
 - Regular monitoring of vital signs, physical condition, and body weight measurements.
 - Clinically significant infections (confirmed by culture, biopsy, genomic, radiologic, or serologic findings) that requires hospitalization or active anti-microbial treatment will be tabulated as incidence rates per tacrolimus formulation.
 - Cytomegalovirus (CMV), BK Virus, and Epstein-Barr disease will be tabulated as incidence rates per tacrolimus formulation.
 - dnDSA and rejection events are collected as part of standard of care in MTA-K
 - Estimated glomerular filtration rate (eGFR) will be estimated using the MRDR formula.
- Patient-Reported Measures: Patients will complete surveys on their own unless they are unable to. Surveys will be administered electronically so that data will be recorded in the study's database immediately and securely. The following patient reported outcomes measures will be assessed at both study visits.
 - HRQoL: PROMIS -29 profile (29 questions) measuring depression, anxiety, fatigue, pain interference, sleep disturbance, physical function, participation in social roles, and pain intensity
 - Symptoms: Calcineurin-inhibitor related symptoms (5 items) and the Transplant related symptoms (15 items) – items from PRO-CTCAE or in PRO-CTCAE format.
 - Symptoms/Tolerability: FACT- G (GP5) – Single item bothersome assessment (1 question).
- Adherence/Medication Satisfaction Measures: The following adherence tools/measures will be assessed at each study visit throughout the study for those patients capable of using an adherence measurement via a digital capture system:
 - The PROMIS Self-Efficacy for Managing Medication and Treatment (26 questions) – (study visit 1 only).
 - The Transplant Satisfaction Questionnaire for Medication – question 14.

Clinical Study Protocol [#SIMPLE]

Table of Contents

SYNOPSIS.....	3
PROTOCOL	9

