Demographics	X		
Medical History	X		
Adverse Event Assessment		X	X
Physical exam including vital signs and weight	X	X	X
Safety labs ¹	X	X	X
Tacolimus trough levels		X	X
Data collection from medical records pertaining to infection, immunosuppression, and graft function	X	X	X
Patient Reported Outcome Assessments			
PROMIS – Self-Efficacy for Managing Medications and Treatments v1.0 (26 items)	X		
PROMIS-29 Profile 2.1 (29 items)	X	X	X
Calcineurin Inhibitor Related Symptoms (CIRS) - (5 PRO-CTCAE items)	X	X	X
Transplant Specific(14 PRO-CTCAE items)	X	X	X
Patient Satisfaction: Treatment Satisfaction Questionnaire for Medication-Question 14 (1 question)			X
FACT-G (GP5)	X	X	X

1 Safety Labs (CBC with differential, Electrolytes including creatinine and eGFR)

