24. APPENDIX 1: CALCINEURIN INHIBITOR RELATED SYMPTOM (CIRS) QUESTIONNAIRE

CALCINEURIN INHIBITOR RELATED SYMPTOMS

Version 1.0

English

As individuals go through treatment for their transplant they sometimes experience different symptoms and side effects. For each question, please check or mark an "x" in the one box that best describes your experiences over the past 7 days...

1.	In the last 7 days, what was the SEVERITY of your TREMBLING HANDS at its WORST?				
 None  Mild  Moderate  Severe  Very severe					
In the last 7 days, how much did TREMBLING HANDS INTERFERE with your usual or daily activities?					
 Not at all  A little bit  Somewhat  Quite a bit  Very much					
2.	In the last 7 days, what was the SEVERITY of your MUSCLE CRAMPS at its WORST?				
 None  Mild  Moderate  Severe  Very severe					
In the last 7 days, how much did your MUSCLE CRAMPS INTERFERE with your usual or daily activities?					
 Not at all  A little bit  Somewhat  Quite a bit  Very much					
3.	In the last 7 days, what was the SEVERITY of your MUSCLE WEAKNESS at its WORST?				
 None  Mild  Moderate  Severe  Very severe					
In the last 7 days, how much did your MUSCLE WEAKNESS INTERFERE with your usual or daily activities?					
 Not at all  A little bit  Somewhat  Quite a bit  Very much					
4.	In the last 7 days, what was the SEVERITY of your SWOLLEN GUMS at their WORST?				
 None  Mild  Moderate  Severe  Very severe					
5.	In the last 7 days, what was the SEVERITY of your INCREASED HAIR GROWTH at its WORST?				
 None  Mild  Moderate  Severe  Very severe					

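### Synopsis secondary endpoint 3 does not count a severe CIRS item that resolves to 0, and endpoints 3 and 4 stand only in the synopsis with no planned analysis

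*Combined protocol and SAP*

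**What the plan says.** **Synopsis, Secondary Endpoints.** Endpoint 3 is the percentage of patients with a CIRS item that drops "from a severe or very severe score (3 to 4) to a mild to moderate (1 or 2) score from 4 to 12 months". Endpoint 4 is "Total percent of patients with a reduction in any single CIRS item by 1 point or greater from 4 to 12 months". Neither names a denominator or mentions the treatment groups. Endpoint 2 does name the groups: "Total percent of patients in each treatment group with a severe or very severe score (3 or 4) on any CIRS item 12 months".

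**Scale.** The synopsis says of the CIRS: "Each symptom is based on symptom severity in the last 7 days scaled from 0 (none) – 4 (very severe". In Appendix 1 the first item asks "In the last 7 days, what was the SEVERITY of your TREMBLING HANDS at its WORST", and the answers run from None to Very severe. The severity question for each of the other four items offers the same answers.

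**Timing.** The plan is to "survey these patients at baseline (first 30 days post-transplant), at 4 months, and at 12 months post-transplantation". The Schedule of Events marks the row "Calcineurin Inhibitor Related Symptoms (CIRS) - (5 PRO-CTCAE items" at all three visits.

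**Section 3 (Objective and Endpoints).** It lists ten secondary endpoints where the synopsis lists twelve. Endpoint 2 is in both lists; synopsis endpoints 3 and 4 are in the synopsis alone.

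**Section 17 (Statistical Analyses).** CIRS scores are analysed as change from enrollment to month 12, by ANCOVA adjusted for the baseline score. The item-level classification (improved, worsened, unchanged) covers transplant-related symptoms and GP5, not CIRS items. No analysis is given for endpoints 2, 3 or 4.

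**Comparison.** For the primary objective, "a standard two-group design will be used to compare treatment groups". Under Section 8 the formulation is chosen by the care team; nothing is randomised by the study.

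**The concern.** The best outcome for a severe symptom is that it disappears. Endpoint 3 stops at 1, so a programmer who follows the text leaves that outcome out of the numerator. Endpoint 4, on the next line, includes it. The two endpoints then disagree on the same patient, and endpoint 3 understates improvement most in a group where symptoms clear completely.

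Nothing elsewhere repairs the wording, because Section 3 omits both endpoints and Section 17 does not analyse them. At stake is a published secondary result that understates benefit and, in some circumstances, points the wrong way.

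**Working it through.** The documents give no rate, sample size or power for endpoints 3 and 4, so there is no figure to reproduce. Step 1 rests on the text alone. Steps 2 and 3 use assumed rates.

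**Step 1. Classify an item scored 4 at month 4.**

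| Month-12 score | Endpoint 3 | Endpoint 4 | Severe at month 12 (endpoint 2) |
|---|---|---|---|
| 0 | not counted | counted | no |
| 1 or 2 | counted | counted | no |
| 3 | not counted | counted | yes |
| 4 | not counted | not counted | yes |

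The first row is the fault. At patient level, endpoint 3 needs only one qualifying item, which has two consequences:
- A patient with two severe items that both reach 0 is not counted.
- A patient with one item falling from 4 to 2 and another staying at 4 is counted, yet is still severe under endpoint 2.

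A patient whose item reaches 0 is still counted if another severe item falls to 1 or 2. The loss therefore concerns patients whose only improvement out of the severe range was to 0.

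**Step 2. Size of the omission.** Assume one severe item per patient, no new severe items after month 4, and 30% severe at month 4 in both groups. Of the severe patients, 50% (immediate release) and 60% (Envarsus XR) improve to 2 or less. Of the improvers, 20% (immediate release) and a share x (Envarsus XR) reach 0.

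- Endpoint 3 as written, over all patients: 0.30 × 0.5 × (1 − 0.2) = 12% for immediate release; 0.30 × 0.6 × (1 − x) for Envarsus XR.
- Counting 0 as well: 0.30 × 0.5 = 15% against 0.30 × 0.6 = 18%.
- Severe at month 12: 0.30 × 0.5 = 15% against 0.30 × 0.4 = 12%.

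| x | Immediate release | Envarsus XR | Ranking as written |
|---|---|---|---|
| 20% | 12% | 14.4% | correct, both under-counted |
| 33% | 12% | 12% | tied |
| 40% | 12% | 10.8% | reversed |
| 50% | 12% | 9% | reversed |
| 60% | 12% | 7.2% | reversed |

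The break-even is x = 1 − (0.5/0.6)(1 − 0.2) = 33%. If the immediate-release share reaching 0 is 10%, 20%, 30% or 40%, it becomes 25%, 33%, 42% or 50%. An at-risk denominator does not cure this: at x = 50% the rates are 0.5 × 0.8 = 40% against 0.6 × 0.5 = 30%.

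**Step 3. Start at month 4.** This step applies only if the groups are compared over all patients.

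- Endpoint 3: assume 30% against 15% severe at month 4, half improving in each group, none to 0. The all-patient rates are 0.30 × 0.5 = 15% against 0.15 × 0.5 = 7.5%, so the group with fewer severe patients looks worse. Among patients severe at month 4 it is 50% against 50%. The all-patient reversal ends once the improvement rate with fewer severe patients exceeds 0.30/0.15 = 2 times the other.
- Endpoint 4: assume five independent items, each present in 50% against 35% of patients, and each present item having a 30% chance of falling. The rates are 1 − (1 − 0.50 × 0.3)^5 = 55.6% against 1 − (1 − 0.35 × 0.3)^5 = 42.6%. Again the less symptomatic group looks worse.

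**The case against.** **It is probably a drafting slip.** The range 1 or 2 may have been meant as 2 or less. That is likely, but the text as it stands would be programmed with the exclusion, and the correction takes one line.

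**Full resolution is not lost to the study.** This stands. A fall from 3 to 0 counts in endpoint 4, lowers the score behind the primary endpoint, and is not severe under endpoint 2. The documents also define no responder, so it is more exact to say that the patient is not counted than that treatment failed.

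**Endpoints 3 and 4 may be leftover text.** Section 3 drops both, Section 17 measures CIRS change from enrollment, and the synopsis window for the donor-specific antibody endpoint (months 4 to 12) becomes the whole 12 months in Section 3. The pattern is suggestive, but the documents do not say which list governs. This supports putting reconciliation first.

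**Stronger readings that the documents do not support.**
- A reader might infer that endpoint 3 will rank the groups wrongly. With equal shares reaching 0 it only under-counts, and the documents give no item-level rates.
- A reader might infer that the month-4 start biases the treatment comparison. Neither endpoint states a between-group comparison or an all-patients denominator. Both would have to be assumed from the general two-group design.
- A reader might infer that endpoint 2 is a sound replacement as it stands. The care team chooses treatment, and endpoint 2 is a month-12 proportion with no baseline adjustment and no analysis in Section 17.

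**Conclusion.** The wording fault is certain: endpoint 3 excludes a valid score, and that score is the best one. The certain effect is to miss any patient whose severe symptom improved only by clearing completely. Reversal of the group ranking is possible, not shown. It needs the improvers in the better group to reach 0 clearly more often, more than 33% against 20% under the assumed rates.

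That both endpoints are absent from Sections 3 and 17 is also a matter of record. The month-4 point is conditional and is a caution for reporting, not a demonstrated bias.

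The impact is minor. Two of twelve synopsis secondary endpoints in a pilot study are affected, and no test is planned for either. The primary endpoint is untouched.

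**What to change.** 1. Reconcile the synopsis with Sections 3 and 17: either drop endpoints 3 and 4, or keep them in corrected form in all three places.
2. If kept, define endpoint 3 as a month-12 score of 2 or less, including 0, on an item scored 3 or 4 at month 4. Report it among patients with such an item. State how several severe items are handled, for example by requiring all of them to be 2 or less.
3. Because month 4 is on treatment, report endpoints 3 and 4 descriptively, beside the month-4 CIRS distribution by group.
4. If endpoint 2 is used to compare severe symptoms between these non-randomised groups, adjust it for the baseline CIRS and state the analysis in Section 17.

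**Cost.** No new data are needed, since the CIRS is already collected at all three visits. Endpoint 3 loses precision in the smaller denominator. Section 17 expects 240 × 0.85 = 204 completers. No allocation ratio is given, so assume 102 per group and a response rate of 50%:
- 30% severe in both groups (about 31 and 31 patients): 1.96 × √(0.25/31 + 0.25/31) = ±25 percentage points.
- 30% against 15% severe (about 31 and 15): 1.96 × √(0.25/31 + 0.25/15) = ±31 points.

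Requiring every severe item to improve would also lower the response rate. If both endpoints are dropped, no listed endpoint explicitly uses the month-4 CIRS survey, which would still be collected.
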